7.4.1.1.1. Dose Adjustments

7.4.1.1.1.1. Abemaciclib

Dose adjustments as outlined in Table JPCG.8 are allowed both within a cycle and between cycles. Abemaciclib must be reduced sequentially by one dose level.

For patients requiring dose reduction(s), any re-escalation to a prior dose level is permitted only after consultation with the Lilly clinical research physician (CRP). After re-escalation, subsequent dose adjustments should be based on the dose of abemaciclib that the patient is currently receiving.

Table JPCG.8. Dose Adjustments of Abemaciclib

Arm	Dose Adjustment	Oral Dose	Frequency
A and B	0	150 mg	Q12H
	1	100 mg	Q12H
	2	50 mg	Q12H
C	0	200 mg	Q12H
	1	150 mg	Q12H
	2	100 mg	Q12H

Abbreviation: Q12H = every 12 hours.

For Arms A and B, if a patient receiving the 50 mg Q12H dose of abemaciclib requires further dose reduction, the patient should be discontinued from study treatment. For Arm C, if a patient receiving the 100 mg Q12H dose of abemaciclib requires a further dose reduction, the patient should be discontinued from study treatment. Based on the judgment of the investigator, if a patient is receiving clinical benefit from study therapy and requires further dose reduction than

what is outlined in [Table JPCG.8](#), the investigator must discuss with Lilly CRP prior to further dose reduction.

For Arm A, in the event that abemaciclib must be discontinued due to tolerability, a patient may continue to receive tamoxifen at the investigator's discretion.

7.4.1.1.1.2. Tamoxifen (Arm A only)

Dose adjustments for tamoxifen are not planned. If a dose of tamoxifen is forgotten, tamoxifen dosing will be continued the following day without change (meaning missed doses will not be made up). See Section [7.4.1.1.2.2](#) for details on dose delays for tamoxifen.

In the event there is evidence of metrorrhagia, rapid gynecological examination should be performed according to local institutional standards. Tamoxifen will be permanently discontinued in the event of a thromboembolic episode or atypical hyperplasia of the endometrium.

If tamoxifen is permanently discontinued due to tolerability, a patient may continue to receive abemaciclib at the investigator's discretion.

7.4.1.1.1.3. Loperamide

Loperamide will be dispensed via IWRS for all patients in all the arms; however, only patients in Arm C should take loperamide prophylactically. Patients in Arms A and B should only take loperamide once the patient experiences diarrhea and requires treatment.

For Arm C, during Cycle 1, prophylactic loperamide should be taken with the first dose of abemaciclib. Loperamide may be discontinued 28 days after the initiation of abemaciclib therapy at the investigator's discretion. However, if the patient develops diarrhea after loperamide discontinuation, loperamide administration should be reinitiated at the investigator's discretion. If abemaciclib dosing is suspended for a reason other than diarrhea, loperamide administration should also be suspended and reinitiated when abemaciclib dosing is reinitiated.

If a patient experiences constipation or other symptoms related to loperamide dosing (for example, abdominal cramping), the investigator may reduce/stop the patient's dosing of loperamide. If a patient does not have a bowel movement for ≥ 36 hours, loperamide is to be suspended until bowel movements resume. If loperamide administration resumes, the dose may be adjusted (e.g. once every other day) at the investigator's discretion. Investigators should take into account patient's history and/or risk of constipation when considering increases in loperamide dosing, more than prophylactic doses taken with abemaciclib.

7.4.1.1.2. Dose Delays and Omission

7.4.1.1.2.1. Abemaciclib

[Table JPCG.9](#) provides general guidelines for dose delays of abemaciclib.

Table JPCG.9. General Dose Delays of Abemaciclib

General Dose Delays	Time Permitted for Delay
Delay of a cycle due to holidays, weekends, bad weather, or other unforeseen circumstances	7 days
Toxicity-time for recovery to baseline or at least Grade 1 for nonhematologic and at least Grade 2 for hematologic toxicity	Up to 14 days

Both dose suspension (within a cycle) and cycle delay are permitted. When a dose suspension or cycle delay occurs related to toxicity (defined as an AE possibly related to study treatment per investigator judgment), abemaciclib and/or tamoxifen (Arm A only) may be suspended or delayed as determined by the investigator's judgment, but only for a maximum of 14 days.

Study treatment may be held up to 14 days within a cycle or at start of next cycle to permit sufficient time for recovery from the toxicity. If a dose suspension occurs within a cycle, the investigator may resume study drug dosing at the same dose level for the remainder of the cycle or, for abemaciclib only, at a reduced dose (assuming resolution to at least Grade 1 for nonhematological and at least Grade 2 for hematological toxicity). If the patient experiences the same toxicity with the same or greater severity (Common Terminology Criteria for Adverse Events [CTCAE] grade) requiring a dose suspension within a cycle or at start of the next cycle, the patient must be dose reduced for abemaciclib and not re-challenged a second time at the prior dose level (see [Table JPCG.7](#)).

Patients not recovering from toxicity within 14 days should be considered for discontinuation of study treatment. In exceptional circumstances, a delay >14 days is permitted upon agreement between the investigator and the Lilly CRP and abemaciclib dose adjustment is to be considered.

A delay of a cycle due to holiday, weekend, bad weather, or other unforeseen circumstances will be permitted for a maximum of 7 days and not counted as a protocol deviation. In exceptional cases of planned delays (including but not limited to vacation or holidays), additional study treatment may be dispensed.

In the event of a cycle delay due to logistical reasons (for example, due to patient availability), the patient should continue on study treatment if the patient has adequate drug supply. If a patient's treatment is interrupted as a result of not having sufficient drug supply, the cycle may be delayed up to 7 days (and not be considered a protocol violation). In exceptional circumstances, a delay >7 days is permitted upon agreement between the investigator and the Lilly CRP.

7.4.1.1.2.2. Tamoxifen (Arm A only)

In the event of the occurrence of Grade 3-4 toxicity related to tamoxifen, tamoxifen dosing should be stopped for a maximum of 14 days. If the toxicity improves during this period, tamoxifen may be resumed, if possible. If the toxicity does not improve within 14 days or recurs upon resumption, tamoxifen should be permanently discontinued. If tamoxifen is permanently

discontinued due to tolerability, the patient may continue to receive abemaciclib at the investigator's discretion.

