7.4. Dosage Modification

7.4.1. Special Treatment Considerations

7.4.1.1. Dose Adjustments and Delays

Table JPCG.7. Toxicity Dose Adjustments and Delays of Abemaciclib

Toxicity Type	Toxicity Profile and Severity	Dose Suspension	Dose Reduction
Hematologic Toxicity Section 7.4.1.1.2.1	Grade 3	Dose MUST be suspended until toxicity resolves to at least Grade 2.	Dose MAY be reduced by 1 dose level - investigator's discretion.
Hematologic Toxicity Section 7.4.1.1.2.1	Recurrent Grade 3	Dose MUST be suspended until toxicity resolves to at least Grade 2.	Dose MUST be reduced by 1 dose level.
Hematologic Toxicity Section 7.4.1.1.2.1	Grade 4	Dose MUST be suspended until toxicity resolves to at least Grade 2.	Dose MUST be reduced by 1 dose level.
Hematologic toxicity: If patient requires administration of blood cell growth factors. Sections 7.4.1.1.2.1 and 7.7.2	Regardless of severity. (Use of growth factors according to ASCO Guidelines)	Dose MUST be suspended for at least 48 hours after the last dose of blood cell growth factors was administered and until toxicity resolves to at least Grade 2	Dose MUST be reduced by 1 dose level unless already performed for incidence of toxicity that led to the use of growth factor
Nonhematologic Toxicity ^b (except diarrhea and ALT increased) Section 7.4.1.1.2.1	Persistent or recurrent Grade 2 that does not resolve with maximal supportive measures within 7 days to baseline or Grade 1	Dose MUST be suspended until toxicity resolves to either baseline or Grade 1.	Dose MUST be reduced by 1 dose level.
Nonhematologic Toxicity Section 7.4.1.1.2.1	Grade 3 or 4	Dose MUST be suspended until toxicity resolves to either baseline or Grade 1.	Dose MUST be reduced by 1 dose level.
Diarrhea Section 7.7.1.1	Grade 2 that does not resolve within 24 hours to at least Grade 1	Dose MUST be suspended until toxicity resolves to at least Grade 1.	Dose reduction is NOT required.
Diarrhea Section 7.7.1.1	Persistent or recurrent Grade 2 that does not resolve with maximal supportive measures or any Grade of diarrhea that requires hospitalization	Dose MUST be suspended until toxicity resolves to at least Grade 1.	Dose MUST be reduced by 1 dose level.
Diarrhea Section 7.7.1.1	Grade 3 or 4	Dose MUST be suspended until toxicity resolves to at least Grade 1.	Dose MUST be reduced by 1 dose level.

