ALT Increased Section 9.4.2.1	Persistent or recurrent ^a Grade 2 (>3.0-5.0×ULN), or Grade 3 (>5.0-20.0×ULN) ^c	Dose MUST be suspended until toxicity resolves to baseline or Grade 1.	Dose MUST be reduced by 1 dose level.
ALT Increased Section 9.4.2.1	Grade 4 (>20.0×ULN)	Abemaciclib therapy MUST be discontinued.	Abemaciclib therapy MUST be discontinued.
ALT Increased with increased total bilirubin, in the absence of cholestasis	Grade 3 increased ALT (>5.0 x ULN) with total bilirubin >2 x ULN	Abemaciclib therapy MUST be discontinued	Abemaciclib therapy MUST be discontinued

Abbreviation: ALT = alanine transaminase; ASCO = American Society of Clinical Oncology.

Note: MUST = mandatory.

- a Determination of persistent events will be at the discretion of the investigator. Recurrent toxicity refers to the same event occurring within the next 8 weeks (as measured from the stop date of the preceding event). This does not include events in the same class (for example, neutropenia followed by anemia 1 month later). As a general guidance, based on the risk/benefit balance assessment per the investigator, for a patient who experiences a new episode of Grade 3 hematological toxicity after more than 8 weeks following the last episode of same Grade 3 hematological toxicity, the investigator may consider resuming the patient on the same drug dose if the patient satisfies the following conditions:
 - shows stable hematological counts (\leq Grade 2) during that timeframe
 - has absence of any infectious sign or risk factor
 - is getting benefit from study treatment
- b Additional guidance for renal and hepatic monitoring is in Section 9.4.2.
- c Grade 3 ALT increased is a trigger for additional assessments and possibly hepatic monitoring. See Section 9.4.2.1 for additional guidance for hepatic monitoring.

Any questions regarding the dose reduction decision should be discussed with the Lilly clinical research physician (CRP).

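### Section 7.4.1.1.2.1 lets abemaciclib restart at the unreduced dose after toxicities for which Table JPCG.7 makes a one-level reduction mandatory

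*Protocol*

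**What the plan says.** Two places set the abemaciclib dose after a toxicity-related suspension.

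**Table JPCG.7 (Section 7.4.1.1)** works by type and grade of toxicity. For a first Grade 4 hematologic event and for Grade 3 or 4 nonhematologic toxicity it orders suspension and then "Dose MUST be reduced by 1 dose level". It does the same for nonhematologic toxicity (other than diarrhea and ALT increase) that is "Persistent or recurrent Grade 2 that does not resolve with maximal supportive measures within 7 days to baseline or Grade 1". For a persistent or recurrent Grade 2 ALT increase, or a Grade 3 one, the suspension entry is "Dose MUST be suspended until toxicity resolves to baseline or Grade 1", again with a mandatory one-level reduction. The table's own note reads "Note: MUST = mandatory". Reduction is left to the investigator for a first Grade 3 hematologic event.

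**Section 7.4.1.1.2.1** is the running text on dose delays. Its rule for a within-cycle suspension is this: "the investigator may resume study drug dosing at the same dose level for the remainder of the cycle". A lower dose is the alternative, and it is open to abemaciclib alone. The condition is recovery of the toxicity to Grade 1 (nonhematologic) or Grade 2 (hematologic). The next sentence covers a repeat of the same toxicity at the same or greater severity that requires suspension: "the patient must be dose reduced for abemaciclib and not re-challenged a second time at the prior dose level". That sentence carries the paragraph's only pointer to Table JPCG.7.

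**The concern.** The same-dose permission takes no account of the grade that caused the suspension. Read as written, it lets an investigator restart the full dose after a first Grade 4 neutropenia once counts have recovered to Grade 2, although the table requires the next level down. The repeat-event sentence reinforces this reading: barring a second rechallenge at the prior dose presupposes that one was allowed.

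The reduction is a safety rule and the table calls it mandatory. Two sites could handle the same event differently and each cite the protocol. The contrast with Section 7.4.1.1.1.1 is also awkward. There, going back up after a reduction needs consultation with the sponsor's physician. Here, the reduction could be skipped with no consultation.

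**Working it through.** No figure in the protocol needs to be reproduced. The check compares the two rules row by row, then reads the size of the gap from Table JPCG.8.

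**Step 1. Compare the rules for a within-cycle suspension of abemaciclib.**

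| Event | Table JPCG.7 | Section 7.4.1.1.2.1 | Result |
|---|---|---|---|
| Hematologic Grade 3, first | reduction optional | same or reduced dose | agree |
| Hematologic Grade 4, first | reduction mandatory | same dose allowed | conflict |
| Nonhematologic Grade 3 or 4, first (not diarrhea or ALT) | reduction mandatory | same dose allowed | conflict |
| Nonhematologic Grade 2, persistent beyond 7 days | reduction mandatory | same dose allowed | conflict |
| ALT Grade 2 persistent, or Grade 3 | reduction mandatory | same dose allowed | conflict |
| ALT Grade 4, or Grade 3 with raised bilirubin and no cholestasis | discontinue | no resumption arises | outside the point |

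**Step 2. Look for text that resolves the conflict.**

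- Diarrhea: Section 7.7.1.1 sends resumed dosing back to Table JPCG.7.
- Growth-factor use: Section 7.7.2 restates the mandatory reduction.
- Suspected renal deterioration: Section 9.4.2.2 points to the table.

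These three are settled and are not part of the point. Cycle delays and tamoxifen are also outside it. For the four conflicting rows there is no equivalent sentence. The hematologic and nonhematologic rows cite Section 7.4.1.1.2.1, so they send the reader to the permission itself. The ALT row cites Section 9.4.2.1, which deals with hepatic monitoring and does not address the resumed dose.

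**Step 3. Size of the gap, from Table JPCG.8.** Daily dose = 2 × the Q12H dose.

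| Arm | Level before event | Restart under the text | Restart under the table | Gap |
|---|---|---|---|---|
| A, B | 150 mg Q12H | 2 × 150 = 300 mg/day | 2 × 100 = 200 mg/day | 100 mg/day |
| A, B | 100 mg Q12H | 2 × 100 = 200 mg/day | 2 × 50 = 100 mg/day | 100 mg/day |
| C | 200 mg Q12H | 2 × 200 = 400 mg/day | 2 × 150 = 300 mg/day | 100 mg/day |
| C | 150 mg Q12H | 2 × 150 = 300 mg/day | 2 × 100 = 200 mg/day | 100 mg/day |

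**Step 4. The lowest level.** For Arms A and B, Section 7.4.1.1.1.1 says "if a patient receiving the 50 mg Q12H dose of abemaciclib requires further dose reduction, the patient should be discontinued from study treatment". The same holds at 100 mg Q12H in Arm C. The exception is a patient with clinical benefit, for whom a further reduction may be discussed with the sponsor's physician. Under Section 7.4.1.1.2.1 the same patient could simply restart at 50 or 100 mg Q12H.

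**The case against.** The strongest reply is that the two texts can be read together. The table is specific and mandatory and sits under the parent heading. The later section gives general guidance on delays and lists the available options, from which the table row selects one. On that reading the same-dose option still has work to do: first Grade 3 hematologic toxicity, Grade 2 diarrhea not resolved within 24 hours, and suspensions for events in no mandatory row. The sentence also covers both study drugs, and part of its purpose may be to make clear that only abemaciclib can be reduced. The repeat-event sentence gives one trigger for reduction without saying there are no others. The paragraph does cite the table, and the text under Table JPCG.7 sends dose-reduction questions to the sponsor's physician.

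Much of this is fair. The combined reading is possible, and many sites would adopt it. It is also fair that this is an inconsistency of drafting more than a design decision, and that the persistent Grade 2 rows are not severe toxicities.

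The reply still does not remove the problem. No sentence gives the table precedence, and the only pointer to it is attached to the repeat event and not to the permission. Where the protocol wants the table to control resumed dosing it says so, as for diarrhea. The route to the sponsor's physician helps only a site that sees a question to ask, and an explicit permission raises none.

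**Conclusion.** The point holds. For the four groups of events marked as conflicts, Section 7.4.1.1.2.1 as written permits a restart that Table JPCG.7 prohibits. The excess is one dose level, 100 mg/day, in every arm and at every step of Table JPCG.8. At the lowest level the difference is between continuing treatment and, in the ordinary case, stopping it.

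This rests on the current wording alone and assumes no event rate. The protocol gives no rates for these events from which affected patients could be counted, so neither a number of patients nor an effect on the PFS comparison is claimed. It should be corrected, because compliance with a mandatory safety rule should not depend on each site reconciling the two texts for itself.

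**What to change.** In Section 7.4.1.1.2.1, qualify the same-dose option for abemaciclib with *unless Table JPCG.7 requires a dose reduction*. Add one sentence stating that Table JPCG.7 governs the abemaciclib dose after toxicity. The tamoxifen wording can stay as it is.

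The cost is one clause and one sentence in a protocol amendment, plus a memo to sites. No new procedures, data or patients are needed.

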7.5. Preparation/Handling/Storage/Accountability

Abemaciclib, tamoxifen, and loperamide will be supplied by Lilly and labeled according to country regulatory requirements. All capsules/tablets should be stored according to their associated product label and taken as indicated. Patients should store these agents in the original package provided and according to the product label (where applicable) and be instructed to keep all medications out of reach of children.

7.6. Treatment Compliance

Patient compliance with abemaciclib will be assessed by reconciliation at qualified visits (e.g. Day 1 of each Cycle). Study medication administration data will be recorded in the patient's medical record and eCRF.

Patients who are significantly noncompliant will be discontinued from the study. A patient will be considered significantly noncompliant if she misses more than 25% cumulative days of abemaciclib (full doses) during the study. Similarly, a patient will be considered significantly noncompliant if she is judged by the investigator to have intentionally or repeatedly taken more than (>125%) the prescribed amount of medication. Abemaciclib dose suspensions or delays related to toxicity may occur and will not result in a patient being considered as noncompliant.

Patients randomized to Arm A, will be assessed by authorized study personnel for noncompliance of tamoxifen. All tamoxifen administration data will be recorded in the patient's medical record and eCRF.

Patients randomized to Arm C will be assessed by authorized study personnel for noncompliance of prophylactic loperamide only during Cycle 1. Prophylaxis during Cycle 2 and beyond is at the discretion of the investigator. All loperamide administration, including but not limited to dose adjustments during Cycle 1, will be recorded in the patient's medical record and eCRF.

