On-Study-Treatment Schedule of Activities

Day within cycle (28 days = 1 cycle)	Cycle 1		Cycle 2		Cycle 3 and beyond (per instructions)	Comments
	1	15	1	15	1	
Procedure						
Biomarker plasma sample	X		X		X	Collect at Cycle 1 Day 1, Cycle 2 Day 1 and Cycle 3 Day 1. See Appendix 4 for details on timing for sample collection
Archived tumor tissue	X					Formalin-fixed paraffin-embedded (FFPE) tumor sample must be requested after study eligibility is confirmed.

Abbreviations: AE = adverse event; CT = computerized tomography; CTCAE = Common Terminology Criteria for Adverse Events (NCI 2009); ECOG = Eastern Cooperative Oncology Group (Oken et al. 1982); EORTC QLQ-C30 = European Organization for Research and Treatment of Cancer Quality of Life Questionnaire-Core 30; mBPI-sf = modified Brief Pain Inventory-short form; MRI = magnetic resonance imaging; PET = positron emission tomography; RECIST v 1.1 = Response Evaluation Criteria in Solid Tumors Version 1.1; SAE = serious adverse event.

Table JPCG.3. Post-Treatment Follow-Up Schedule of Activities

	Short-Term Follow-Up ^a	Long-Term Follow-Up ^b	
Visit	801	802-8XX	
Procedure			Comments
Physical examination	X		Including weight and vital signs (temperature, blood pressure, pulse rate, respiration rate).
Concomitant medication	X		
Adverse event collection	X		CTCAE Version 4.0. After Visit 801, only study protocol or drug-related events are reported. If a patient has an ongoing AE or SAE possibly related to study drug (for instance, abnormal electrolytes), the patient should be followed until the event is resolved, the event is no longer considered to be drug-related, the event becomes stable or returns to baseline, a new treatment is initiated for the patient, or the patient dies or is lost to follow-up. Any subsequent follow-up(s) for AEs will be no more than 30 days \pm 7 in duration.
ECOG performance status	X		
Radiological tumor assessment	X	X	Not required if objective progressive disease is documented while on treatment. Continue to conduct tumor assessment every 8 weeks (-7 days) until patient has objective disease progression or until primary PFS analysis. After the patient has objective disease progression, radiologic tests are no longer required and the patient will continue with postdiscontinuation follow-up for a minimum of every 90 days until death or study completion.

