ECOG = Eastern Cooperative Oncology Group (Oken et al. 1982); EORTC QLQ-C30 = European Organization for Research and Treatment of Cancer Quality of Life Questionnaire-Core 30; mBPI-sf = modified Brief Pain Inventory-short form; MRI = magnetic resonance imaging; PET = positron emission tomography; SAE = serious adverse event.

- ^a Short-term follow-up begins the day after the patient and the investigator agree that the patient will no longer continue study treatment and lasts approximately 30 days (\pm 7 days). No follow-up procedures will be performed for a patient who withdraws informed consent unless she has explicitly provided permission and consent.
- ^b Long-term follow up begins the day after short-term follow up is completed and continues every 90 days until the patient's death or overall study completion.

Table JPCG.4. Continued Access Schedule of Activities

Visit	Study Treatment	Follow-Up ^a	Comments
	501-5XX	901	
Procedure^b			
Adverse event collection	X	X	CTCAE Version 4.0. Assessments to be conducted with each collection and dispensing of study drug (every 28 days) from Visits 501-5XX.
Administer study drug	X		

Abbreviation: CTCAE = Common Terminology Criteria for Adverse Events.

- ^a Continued access follow-up begins 1 day after the patient and the investigator agree that the patient will no longer continue treatment in the continued access period and lasts approximately 30 days (\pm 7 days). No follow-up will be performed for a patient who withdraws informed consent unless she has explicitly provided permission and consent.
- ^b Efficacy assessments will be done at the investigator's discretion based on the standard of care.

3. Introduction

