8.1. Discontinuation from Study Treatment

Patients will be discontinued from study treatment in the following circumstances:

- the patient is enrolled in any other clinical trial involving an investigational product or any other type of medical research judged not to be scientifically or medically compatible with this study
- investigator decision
 - the investigator decides that the patient should be discontinued from the study or study drug
 - if the patient, for any reason, requires treatment with another therapeutic agent that has been demonstrated to be effective for treatment of the study indication, discontinuation from the study drug occurs prior to introduction of the new agent
- patient decision
 - the patient requests to be withdrawn from the study or study drug
 - the patient's designee (for example, parents, legal guardian, or caregiver) requests that the patient be discontinued from study treatment
- sponsor decision
 - Lilly stops the study or stops the patient's participation in the study for medical, safety, regulatory, or other reasons consistent with applicable laws, regulations, and good clinical practice (GCP)
- the patient becomes pregnant during the study. See Section 9.2 regarding regulatory reporting requirements on fetal outcome and breastfeeding.
- the patient is significantly noncompliant with study procedures and/or treatment
- disease progression
- unacceptable toxicity

Patients who are discontinued from study treatment will have follow-up procedures performed as shown in the Schedule of Activities (Table JPCG.3).

For patients who discontinue study treatment without objectively measured progressive disease, continue to evaluate tumor response according to planned tumor assessment schedule by the same method used at baseline and throughout the follow-up periods until patient has objective disease progression or until the study's primary analysis of PFS. After the patient has objective disease progression, radiologic tests are no longer required.

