8.2. Discontinuation from the Study

Patients will be discontinued from the study in the following circumstances:

- participation in the study needs to be stopped for medical, safety, regulatory, or other reasons consistent with applicable laws, regulations, and GCP
- the patient becomes pregnant during the study. See Section 9.2 regarding regulatory reporting requirements on fetal outcome and breastfeeding.
- the investigator decides that the patient should be discontinued from the study
- the patient requests to be discontinued from the study
- the patient's designee (for example, parents, legal guardian, or caregiver) requests that the patient be discontinued from the study.

Patients who discontinue from the study early will have end-of-study procedures performed as shown in the Schedule of Activities (Table JPCG.3).

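### Section 7.6 removes significantly noncompliant patients from the study, whereas Section 8.1 only stops their treatment and keeps scanning them; the passages need reconciling, though the effect on PFS is probably small

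*Protocol*

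**What the plan says.** Section 7.6 (Treatment Compliance) defines significant noncompliance by drug intake: more than 25% of cumulative days of abemaciclib missed, or more than 125% of the prescribed amount taken intentionally or repeatedly. Its consequence is: "Patients who are significantly noncompliant will be discontinued from the study". It carves out one group: "Abemaciclib dose suspensions or delays related to toxicity may occur and will not result in a patient being considered as noncompliant".

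Section 8.1 (Discontinuation from Study Treatment) lists, among reasons to stop treatment, that "the patient is significantly noncompliant with study procedures and/or treatment". It then adds: "For patients who discontinue study treatment without objectively measured progressive disease, continue to evaluate tumor response", on the planned schedule, until objective progression or the primary PFS analysis.

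Section 8.2 (Discontinuation from the Study) does not list noncompliance. It does list an investigator decision to take the patient off the study. It closes: "Patients who discontinue from the study early will have end-of-study procedures performed as shown in the Schedule of Activities (Table JPCG.3").

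For radiological assessment, Table JPCG.3 says: "Continue to conduct tumor assessment every 8 weeks (-7 days) until patient has objective disease progression or until primary PFS analysis". Its footnote a says: "No follow-up procedures will be performed for a patient who withdraws informed consent unless she has explicitly provided permission and consent".

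Appendix 1 defines intention-to-treat so that patients are followed and assessed whether or not they comply with treatment.

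**The concern.** One behaviour has two dispositions. Under Section 8.1 a noncompliant patient without progression stops the drug and is still scanned. Under Section 7.6 she leaves the study. PFS is the primary endpoint and is analysed by intention to treat. If a site acts on Section 7.6 and stops scanning, the patient is censored because of something she did after randomisation. That censoring is avoidable. It may also be informative if patients who stop taking the drug have a different prognosis, and it could differ by arm because the regimens differ and the study is open-label. Analysis rules cannot recover scans that were never taken.

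The protocol's loose terms make the slip easier. Section 8.1's own treatment list includes the case where "the investigator decides that the patient should be discontinued from the study or study drug", although Section 10.3.3.1 reports discontinuation from treatment and from study separately.

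**Working it through.** **1. The passages side by side**

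| Place | Trigger | What ends | Tumour follow-up |
|---|---|---|---|
| 7.6 | Drug intake outside limits | The study | Not stated |
| 8.1 | Noncompliance with procedures and/or treatment (wider) | Study treatment | Continues to progression or primary PFS analysis |
| 8.2 | Not named; investigator decision available | The study | End-of-study procedures, via Table JPCG.3 |
| 9.1.2 | Any stop of treatment without objective progression | – | About every 8 weeks, to the same endpoint as 8.1 |
| Table JPCG.3 | – | – | 8-weekly scans; follow-up withheld only on consent withdrawal |

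**2. One patient traced through.** Take a patient with no progression who misses more than 25% of days for reasons other than toxicity.
- Under 8.1 and 9.1.2 she is scanned 8-weekly, and a later progression counts.
- Under a literal 7.6 the site turns to 8.2, which offers end-of-study procedures. Table JPCG.3 has no column of that name; its columns are short-term follow-up (Visit 801) and long-term follow-up (Visits 802 onward). A site could do Visit 801 and stop. Section 10.3.1.1 and Table JPCG.10 then censor her at the last adequate assessment.

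**3. The plan's own figure.** Inputs from Section 10.1: HR 0.667, one-sided alpha 0.10, power 80%, 1:1 between Arms A and C.
- Events (Schoenfeld) = 4(1.2816 + 0.8416)² / (ln 0.667)² = 4 × 4.508 / 0.1640 ≈ 110. This reproduces the stated figure.
- Power at 110 events = Φ(0.405 × √(110/4) − 1.2816) = Φ(0.842) = 0.80.
- The analysis is triggered by 110 events (Section 5.3), so lost events first delay it. Power falls only if 110 cannot be reached.
- Slack is limited: 150 × 0.70 = 105 events at the assumed 30% censoring, and 110 events require censoring of at most 40/150 = 26.7%.

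**4. Illustration under assumed rates.** The protocol gives no noncompliance rate. A large-sample exponential simulation scaled to 75 per arm used medians of 9 and 6 months (Section 10.1). All else is assumed: uniform accrual over 12 or 18 months; the criterion met at months 1 to 6; removal if event-free; noncomplier hazard 1, 1.5 or 2 times that of others. The literal 7.6 reading censors everyone at removal. The 8.1 reading censors only the share who start new anticancer therapy, as Table JPCG.10 requires, and follows the rest. Each reading is analysed at its own 110th event.

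| Share starting new therapy | Delay of 110th event, 5% to 10% noncompliant per arm |
|---|---|
| None | 1.0 to 2.3 months |
| Half | 0.5 to 1.3 months |
| Three quarters | 0.3 to 0.7 months |

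With equal removal in both arms, the A/C hazard ratio moves by at most 0.005. For unequal removal (12-month accrual), the hazard ratio under 8.1 → under 7.6 is:

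| Noncompliance, hazard | No one starts new therapy | Three quarters start |
|---|---|---|
| A 5%, C 15%, ×1.5 | 0.642 → 0.654 | 0.651 → 0.654 |
| A 15%, C 5%, ×2 | 0.716 → 0.688 | 0.696 → 0.688 |

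The SE of the log hazard ratio at 110 events is √(4/110) = 0.191. In the first column the shifts are ln(0.654/0.642)/0.191 ≈ 0.10 SE and ln(0.716/0.688)/0.191 ≈ 0.21 SE. The move is toward the null if Arm C loses more patients, and away from it if Arm A does.

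These overstate the effect even at the assumed rates. Every site is taken to apply 7.6 literally, and no death after removal is counted. Table JPCG.10 counts a death as a PFS event unless it comes two or more scan intervals after the last adequate assessment or randomisation.

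**The case against.** The strongest reply is that follow-up is already protected. A patient taken off the study has also stopped study treatment, so the scan duties in Sections 8.1 and 9.1.2 apply to her on their face, and neither exempts study leavers. Even the literal route through Section 8.2 leads to Table JPCG.3, which contains the 8-weekly scans and withholds follow-up only on consent withdrawal. The investigator-decision ground in Section 8.2 also gives Section 7.6 a possible route, so its absence from that list is not decisive. And the triggers are not identical: a patient who does not comply with procedures may miss scans under either section.

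Most of this stands, and it keeps the point minor. It does not remove it. Section 8.2 never says that serial scans continue after a patient leaves the study, and its label matches no column of the table it cites. The instruction in Section 7.6 still differs from that in Section 8.1.

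A reader might infer that the protocol orders scanning to stop, that OS data are lost, or that the trial loses power. The documents support none of these. No passage tells sites to stop scanning. Section 9.1.2 continues survival collection on all patients, and Section 8.3 seeks survival status for those lost to follow-up. The analysis waits for 110 events.

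**Conclusion.** Wrong as written: an internal contradiction between Section 7.6 and Section 8.1, of minor severity. The wording conflict is certain. The PFS consequence is conditional on a site reading Section 7.6 literally against Sections 8.1 and 9.1.2.

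Its size and direction cannot be derived from the protocol. It is probably small, because the affected group is narrow: toxicity-related suspensions and delays are exempt, patients who start new anticancer therapy without progression or death within 14 days are censored under either reading, and early deaths still count as events. The delays and hazard-ratio shifts above are upper-end illustrations for the rates assumed, not estimates. A reader might take them as evidence of material bias in the A versus C comparison; they are not, since every noncompliance rate, timing and hazard multiplier in them is assumed.

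**What to change.** Reconcile Section 7.6 with Sections 8.1 and 8.2, so that it is clear whether noncompliance ends study treatment or study participation. Add one sentence to Section 7.6: for noncompliant patients, tumour assessments and survival follow-up continue per Table JPCG.3 unless the patient withdraws consent. What noncompliance should mean for treatment is for the sponsor to reconcile and is not proposed here.

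The cost is a short wording amendment. No visits or procedures are added, because those needed are already in Table JPCG.3.
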